## 1.3 SCHEDULE OF ACTIVITIES

Procedures	Day 1 (prior to or on day of hospital discharge) a	Week 2 to Week 6 after study enrollment	Telephone Study Visit every 6 months (+/- 4 weeks)	Final Telephone Study Visit (+ 2 weeks after at least 80 ischemic events accrued)
Informed Consent	X			
Inclusion/Exclusion Criteria	X			
Clinical Characteristics	X			
Enrollment	X			
Anti-thrombotic Medication Review	X		X	X
Blood Sample to Quantify FcγRIIa b	X	X d		
Assess for Study Endpoints c			X	X
Complete Case Report Forms (CRFs)	X		X	X
	
a: Procedures can be done at any time after confirmation of myocardial infarction index event and prior to hospital discharge. Day 1 is defined as the day the subject is enrolled into the study and must occur prior to or on the day of hospital discharge.
 
b: Approximately 3 ml to 6 ml blood sample. Blood can be taken up to 2 weeks post-study enrollment.
 
c: Endpoints include Ischemic events (MI, stroke, death) and clinically significant bleeding BARC type 2-5.
 
d: For sites participating in the substudy, a 3 ml to 6 ml blood sample will be drawn 2 to 6 weeks after enrollment into the study
			

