### **Prior study to evaluate FcγRIIa**

[name] et.al. completed a single center prospective trial designed to determine whether platelet expression of FcγRIIa would discriminate cardiovascular risk ([name] 2018). Patients (n=197) were enrolled shortly before discharge from a hospitalization for MI (both ST elevation and non-ST elevation were included). Although inclusion criteria allowed patients who

had been treated with PCI, coronary artery bypass grafting, or medically, all patients enrolled were treated with PCI. The primary endpoint, a composite of MI, stroke, death, and coronary revascularization, was lower in patients with platelet expression of FcγRIIa <11,000 (Figure 3). All patients were treated with ASA (81 mg) and treatment with clopidogrel (~64%) and ticagrelor (~36%) was balanced in patients with high and low platelet expression of FcγRIIa (Serrano 2007).

[figure not shown]

Figure 3: Summary of prospective single center study ([name] 2018)  
CVA=cerebrovascular accident, MI=myocardial infarction, Revasc=revascularization

Clinical characteristics of patients with high and low platelet expression of FcγRIIa were well balanced with the exception of older age, diabetes, and prior revascularization being more prominent in the high expression group. Cox multivariate analysis for the combination of MI, stroke, revascularization, and death demonstrated a hazard ratio of 3.0 ( $p=0.02$ ) for platelet expression of FcγRIIa  $>11,000$  when age, diabetes, and prior revascularization were included as covariates.

The incidence of revascularization was similar in patients with high and low platelet expression of FcγRIIa (low platelet FcγRIIa n=3, 3.2%; high platelet FcγRIIa n=4, 3.8%,  $p=0.815$ ). Patients with platelet expression of FcγRIIa  $\geq 11,000$  had a greater risk of MI, stroke, and death that became apparent after 6 months (Figure 4).

Cox regression analysis was performed and platelet expression of FcγRIIa was the sole covariate (hazard ratio 3.9,  $p=0.035$ ) associated with freedom from MI, stroke, and death.

[figure not shown]

Figure 4: Kaplan-Meier curves of the probability of freedom from MI, stroke, and death. The average duration of follow-up was 20 months (range 6-29 months).

MI=myocardial infarction

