#### 9.4.2 ANALYSIS OF THE PRIMARY OBJECTIVE

Cox proportional hazards models will be fit to compare the risk of the primary endpoint based on platelet expression of FcγRIIa as a continuous variable. Subjects will be followed until their earliest MI, stroke, or death. Patients who do not experience the composite endpoint will be censored at their last telephone follow-up. Time to the primary endpoint will be calculated as days from study enrollment. Models will be adjusted for potential confounders including sex and other subject demographics and medical history collected at baseline. In the pilot study, it was observed that older age, diabetes mellitus, and prior revascularization were associated with higher platelet FcγRIIa expression.

A set of sensitivity analyses will evaluate FcγRIIa as a binary endpoint, which each analysis using a different threshold for classifying FcγRIIa as high or low. In particular, these analyses will explore whether a binary or a continuous measure of FcγRIIa provides greater predictive value, and whether or not a threshold of  $\geq 11,000/\text{platelet}$  is optimal.

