## 12 APPENDIX 1 – STUDY ENDPOINT EVENT DEFINITIONS

### Definition for Acute Myocardial Infarction (types 1, 2 and 3 MI) [Thygesen 2018]

The term acute myocardial infarction should be used when there is acute myocardial injury with clinical evidence of acute myocardial ischemia and with detection of a rise and/or fall of cTn values with at least 1 value above the 99th percentile URL and at least 1 of the following:

- Symptoms of myocardial ischemia;
- New ischemic ECG changes;
- Development of pathological Q waves;
- Imaging evidence of new loss of viable myocardium or new regional wall motion abnormality in a pattern consistent with an ischemic etiology;
- Identification of a coronary thrombus by angiography or autopsy (not for types 2 or 3 MIs).

Postmortem demonstration of acute atherothrombosis in the artery supplying the infarcted myocardium meets criteria for type 1 MI. Evidence of an imbalance between myocardial oxygen supply and demand unrelated to acute atherothrombosis meets criteria for type 2 MI. Cardiac death in patients with symptoms suggestive of myocardial ischemia and presumed new ischemic ECG changes before cTn values become available or abnormal meets criteria for type 3 MI.

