## Bleeding Academic Research Consortium (BARC) Definition for Bleeding [Mehran 2011]

Type 0: no bleeding

Type 1: bleeding that is not actionable and does not cause the patient to seek unscheduled performance of studies, hospitalization, or treatment by a healthcare professional; may include episodes leading to self-discontinuation of medical therapy by the patient without consulting a healthcare professional

Type 2: any overt, actionable sign of hemorrhage (eg, more bleeding than would be expected for a clinical circumstance, including bleeding found by imaging alone) that does not fit the criteria for type 3, 4, or 5 but does meet at least one of the following criteria: (1) requiring nonsurgical, medical intervention by a healthcare professional, (2) leading to hospitalization or increased level of care, or (3) prompting evaluation

Type 3:

Type 3a:

Overt bleeding plus hemoglobin drop of 3 to  $<5$  g/dL\* (provided hemoglobin drop is related to bleed)

Any transfusion with overt bleeding

Type 3b:

Overt bleeding plus hemoglobin drop  $\geq 5$  g/dL\* (provided hemoglobin drop is related to bleed)

Cardiac tamponade

Bleeding requiring surgical intervention for control (excluding dental/nasal/skin/hemorrhoid)

Bleeding requiring intravenous vasoactive agents

Type 3c:

Intracranial hemorrhage (does not include microbleeds or hemorrhagic transformation, does include intraspinal)

Subcategories confirmed by autopsy or imaging or lumbar puncture

Intraocular bleed compromising vision

Type 4: CABG-related bleeding

Perioperative intracranial bleeding within 48 h

Reoperation after closure of sternotomy for the purpose of controlling bleeding

Transfusion of  $\geq 5$  U whole blood or packed red blood cells within a 48-h period†

Chest tube output  $\geq 2$  L within a 24-h period

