5.7 Statistical Methods

5.7.1 Analysis of the Primary Objective

The primary analysis of the primary endpoint will be a Cox proportional hazards model. The dependent variable is the number of days from enrolment to the occurrence of a primary endpoint, with censoring at the last day of complete follow-up; independent variables will be FcγRIIa (measured in thousands), age in years, history of diabetes mellitus, prior revascularization, multi-vessel coronary artery disease (MVD) defined as ≥2 vessels or left main with a stenosis ≥50%, chronic kidney disease (CKD) defined as estimated glomerular filtration rate (GFR) < 60 ml/min/1.73 m², prior MI, hypertension, tobacco use, heart failure or LVEF<30%, previous stroke or transient ischemic attack, and peripheral arterial disease. Interest is in the FcγRIIa parameter: point estimate (increase in risk per 1000-unit increase in FcγRIIa), confidence interval and p-value. FcγRIIa will be declared to be associated with cardiovascular risk if the 2-sided p-value from this model is < 0.05.

A set of exploratory/sensitivity and subgroup analyses based on the Cox model will also be conducted.

- Instead of censoring at the last day of complete follow-up, censor at the last day of vital status follow-up
- FcγRIIa as the only covariate in the model
- Separate analyses of each component of the primary endpoint: MI and stroke, both censored at the last day of complete follow-up, and death, censored at the last day of vital status follow-up
- Run the primary model in subgroups defined by age (in decades), sex, history of diabetes and prior revascularization (including all covariates except the subgroup variable in the model)
- Run the primary model with the use of DAPT (any use prior to a primary endpoint), and its interaction with FcγRIIa, as additional covariates

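### Whether a bleed during the index stay is an endpoint depends on the day of enrolment, and Appendix 1 has no rule that separates a new MI from the index MI

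*Protocol*

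**What the plan says.** **Enrolment window.** Footnote a of the Schedule of Activities (Protocol 1.3) allows enrolment from confirmation of the index MI: "Procedures can be done at any time after confirmation of myocardial infarction index event and prior to hospital discharge". It adds that "Day 1 is defined as the day the subject is enrolled into the study", and that day need only fall on or before discharge.

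**Time origin.** Protocol 9.4.2: "Time to the primary endpoint will be calculated as days from study enrollment". SAP 5.7.1: "The dependent variable is the number of days from enrolment to the occurrence of a primary endpoint". Protocol 9.4.3 and SAP 5.7.2 reuse that adjusted Cox model for bleeding and name no other origin. No blanking period, discharge landmark or early-event sensitivity analysis appears in the protocol or in the SAP text supplied.

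**MI endpoint.** Appendix 1 requires "detection of a rise and/or fall of cTn values with at least 1 value above the 99th percentile URL" together with one ischemic feature, for example "Development of pathological Q waves". The heading limits the definition to types 1, 2 and 3. Inclusion criterion 1 sends the reader to the same appendix for the index MI.

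**Bleeding endpoint.** BARC type 2-5. Type 2 includes overt bleeding that prompts evaluation or more care, type 3a includes any transfusion with overt bleeding, and the list includes "Type 4: CABG-related bleeding". The closing note says that a bleed close in time to CABG that does not meet type 4 criteria is not a bleeding event.

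**Confirmation.** Endpoints are asked about at the 6-monthly and final calls. The site investigator confirms them from records, and source documents go to the sponsor. No separate committee adjudicates (Protocol 4.1, 10.6).

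**The concern.** The marker is meant to predict what happens after the index MI, and the bleeding question is whether high FcγRIIa carries extra bleeding risk. During the index stay, bleeding is driven largely by arterial access, procedural anticoagulation and surgery. If such bleeds count for subjects enrolled early and not for those enrolled late, part of the endpoint measures when a site enrols its patients. The study plans about 10-20 sites.

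The direction matters. Hypothesis 3 (Protocol 9.1) is that FcγRIIa is not associated with major bleeding. Events unrelated to the marker push the estimate toward that answer, so this weakness favors the expected conclusion.

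The MI definition has a parallel gap. A subject enrolled early, whose troponin is still falling and who then develops Q waves, satisfies each written element without a second infarction. Such an event would enter the primary composite, end that subject's time at risk in a first-event analysis, and count toward the 80 events required before the study may stop.

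The pilot that this study is meant to confirm did not have the same exposure, because its patients "were enrolled shortly before discharge from a hospitalization for MI".

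**Working it through.** **1. The rules applied to two identical subjects.** Both have PCI during the index stay and an access-site bleed that needs a transfusion (BARC 3a).

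| | Subject A | Subject B |
|---|---|---|
| Enrolled | Day the index MI is confirmed, before PCI | Day of discharge |
| Bleed relative to Day 1 | After | Before |
| Bleeding endpoint as written | Yes | No |

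With a CABG bleed in place of the PCI bleed, the same contrast holds only if type 4 criteria are met. Below that severity the Appendix 1 note removes the event for both subjects.

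**2. The MI wording.** Falling troponin with one value above the limit meets the biomarker element. New Q waves meet the second element. The definition has no re-rise, minimum interval or statement that the index MI is excluded. Procedure-related MI (types 4 and 5) lies outside the heading.

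**3. Scale for bleeding.** The plan assumes 5% bleeding in the low group and a ratio of 1.93, so 5% × 1.93 = 9.65% in the high group. With 400 per group (an equal split is my assumption) that gives 400 × (0.05 + 0.0965) = 58.6 bleeds. Suppose a further fraction q of each group has an index-stay bleed unrelated to FcγRIIa. The ratio becomes (9.65% + q)/(5% + q). Power uses the two-proportion normal approximation at two-sided 0.05:

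Φ{[|p₂ − p₁|√n − 1.96√(2p̄(1 − p̄))] / √(p₁(1 − p₁) + p₂(1 − p₂))}, with n = 400.

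| q (assumed) | Extra bleeds, 800 × q | Ratio | Power |
|---|---|---|---|
| 0 | 0 | 1.93 | 71% |
| 0.2% | 1.6 | 9.85/5.2 = 1.89 | 70% |
| 1% | 8 | 10.65/6 = 1.775 | 66% |
| 2% | 16 | 11.65/7 = 1.66 | 62% |
| 5% | 40 | 14.65/10 = 1.465 | 52% |

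q is the share enrolled before their procedure multiplied by the risk of a BARC 2-5 bleed after it. For example, 10% × 2% = 0.2%. The documents give neither factor. The 71% at q = 0 does not match the plan's stated 95% for this comparison. That is a separate matter and does not affect the ratios.

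**4. Scale for the primary composite.** Take 80 events (the planned minimum), a true hazard ratio of 2 and an equal split. If k of the 80 are index-related and unrelated to FcγRIIa, the apparent ratio is approximately [(80 − k) × 2/3 + k/2] / [(80 − k)/3 + k/2]. Power by Schoenfeld's formula is Φ[√(80/4) × ln(ratio) − 1.96].

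| k (assumed) | Apparent ratio | Power |
|---|---|---|
| 0 | 53.33/26.67 = 2.00 | 87% |
| 4 | 52.67/27.33 = 1.93 | 84% |
| 8 | 52/28 = 1.86 | 79% |

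This treats FcγRIIa as high versus low. The planned primary model uses it as a continuous variable, so the table shows direction and rough scale only.

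**The case against.** The strongest reply is that an investigator would not record the qualifying infarct as its own recurrence. The protocol names it the index event, states its target as later events, and asks about endpoints only at telephone visits, the first of them 6 months after enrolment. A patient is unlikely to report Q waves on the second hospital day as a new heart attack, and the sponsor sees the source documents. This stands, and it makes the MI route unlikely. It does not supply the missing criterion, and any protection rests on unwritten judgment that can differ between sites. It helps less for bleeding: a patient may well report a hospital bleed that needed transfusion, the records would confirm it, and the definition includes it.

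Second, eligibility may delay enrolment. Multivessel disease is one of the risk factors and is assessed at angiography. Other pairs, such as age 65 or over with diabetes, qualify without it. The documents do not say how many subjects enrol before a procedure.

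A reader might go further in three ways that the documents do not support:

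- **That all procedural events count.** CABG-related bleeds below type 4 severity are already excluded, and MI types 4 and 5 are outside the stated scope.
- **That the clock for death and stroke should also move to discharge.** No contamination of either by the index MI is shown. The change would remove genuine in-hospital events from the primary endpoint and limit that analysis to survivors to discharge. Enrolment is a legitimate prespecified origin.
- **That a stated share of bleeds is procedural.** No in-hospital rate is given, so any single percentage is invented.

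**Conclusion.** The point holds for bleeding and, more weakly, for MI. As written, the same PCI-related type 2-3 bleed or type 4 CABG bleed is or is not an endpoint according to the day of enrolment. The MI definition does not separate a new infarction from the index one, but counting the index MI is improbable given how endpoints are ascertained.

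The size is unknown. Under the assumed range of 0.2% to 2% index-stay bleeds in both marker groups, the planned ratio of 1.93 becomes 1.89 to 1.66; the lower end is negligible. For the primary composite, 4 misattributed events among 80 would lower a ratio of 2.00 to 1.93, and even that number may not occur.

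The direction toward no association assumes that index-stay bleeds are unrelated to FcγRIIa. In the pilot, high expression went with older age, which could act the other way, although the model adjusts for age. In either case the definition should not depend on the enrolment day. The correction is worth making because it is cheap and because the likely error favors hypothesis 3.

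**What to change.** 1. **Appendix 1.** State that an endpoint MI must be a new event distinct from the index MI, with a new troponin rise from a stable or falling level. Apply this to the endpoint only, because inclusion criterion 1 uses the same appendix for the index MI.
2. **Protocol 9.4.3 and SAP 5.7.2.** Count BARC 2-5 bleeding from index-hospital discharge. List bleeds between enrolment and discharge separately, and keep subjects who had one at risk afterwards. Keep the from-enrolment analysis as a sensitivity analysis.
3. **SAP 5.7.1.** Keep enrolment as the time origin for the primary composite. Add a sensitivity analysis that starts at index discharge.

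The cost is wording in two documents and the index discharge date, which is in the hospital record and may need one added eCRF field. Enrolment practice does not change. The downside is that a few genuine in-hospital bleeds move out of the main bleeding analysis into a separate table and the sensitivity analysis.

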## 2 INTRODUCTION

### 2.1 BACKGROUND

The American Heart Association estimates that during 2020 approximately 720,000 Americans will have a first coronary event (defined as first hospitalized myocardial infarction (MI) or coronary heart disease death), and approximately 335,000 will have a recurrent event (Benjamin 2019). A retrospective cohort study of 78,085 Medicare beneficiaries  $\geq 66$  years of age found that 20.6% of patients with MI had at least one re-hospitalization during the 10 years after their index MI (Levitian 2016).

According to Patel and colleagues, a diverse array of therapeutic options is available to clinicians (Patel 2018) and they propose that what is needed now is effective precision medicine strategies to enable clinicians to target patients with high residual risk with more powerful therapy (Patel 2018). The current study is designed to use translational research to develop biomarkers that may effectively guide individualized therapy based on the hypothesis that platelet expression of Fc $\gamma$ RIIa will identify patients at high and low risk of subsequent MI, stroke, and death. Validation of platelet expression of Fc $\gamma$ RIIa as a biomarker of residual cardiovascular risk will support subsequent studies designed to use platelet expression of Fc $\gamma$ RIIa as a precision medicine tool.

### **Strategies to Reduce Recurrent Ischemic Events/Bleeding**

Strategies designed to reduce the risk of recurrent ischemic events and bleeding are predicated on the following assumptions: 1) The benefit-risk of a treatment should be assessed by comparing the absolute risk differences of the benefit and harm endpoints. 2) A treatment's benefit is generally consistent across population on a relative scale. For this reason, on an absolute scale, benefit is generally greater in high-risk populations. 3) A treatment's harm is generally consistent across populations on an absolute scale. For this reason, benefit-risk is generally greater in a high-risk population. 4) Accordingly, a marker that identifies a high-risk population can enable a treatment to be used in a way that increases its benefit-risk profile. One strategy designed to reduce the risk of recurrent ischemic events is the continuation of dual antiplatelet therapy (DAPT). Two large multicenter randomized trials have demonstrated that long-term DAPT reduces the risk of subsequent cardiovascular events. Treatment with aspirin (ASA) plus clopidogrel reduced the risk of major adverse cardiovascular and cerebrovascular events from 5.9% with ASA monotherapy to 4.3% ( $p<0.001$ ) with ASA plus clopidogrel (Mauri 2014). Continued DAPT increased the risk of moderate or severe bleeding (2.5% vs. 1.6%,  $p=0.001$ ). Treatment with ASA plus ticagrelor (60 mg twice daily) reduced the risk of cardiovascular events to 7.8% compared with 9.0% with ASA alone (Bonaca 2015). The risk of Thrombolysis in Myocardial Infarction (TIMI) major bleeding was higher with ticagrelor (2.3% with 60 mg twice daily) compared with ASA alone (1.1%). Accordingly, the benefits of long-term treatment with DAPT are at least partially offset by an increase in bleeding. Because of this trade-off, the use of DAPT long-term is limited. The promise of precision medicine is to reduce the overall incidence of bleeding by individualizing therapy, targeting patients with high residual cardiovascular risk for long-term DAPT.

The “Ticagrelor with or without Aspirin in High-Risk Patients after PCI (TWILIGHT)” study tested a strategy of ticagrelor monotherapy compared with aspirin plus ticagrelor and demonstrated a reduced risk of bleeding events without an increase in ischemic events with ticagrelor monotherapy (Mehran 2019). While this strategy reduced bleeding, it did not provide guidance on which patients will derive the greatest benefit from long term treatment with more powerful antiplatelet therapy. Further, because treatment with more powerful anti-thrombotic therapies has been consistently associated with a greater incidence of bleeding, it is likely that monotherapy with ticagrelor will be associated with greater bleeding than ASA monotherapy.

A strategy designed to limit the risk of bleeding events is the early transition from DAPT to ASA monotherapy. The 6-month versus 12-month or longer dual antiplatelet therapy after percutaneous coronary intervention (PCI) in patients with acute coronary syndrome (SMART-DATE) randomized patients with acute coronary syndrome (ACS) to either 6 months of DAPT or at least 12 months of DAPT (Hahn 2018). MI (1.8% vs 0.8%; p=0.02) and stent thrombosis (1.1% vs 0.7%, p=0.09) were more common in the 6-month DAPT group. Bleeding Academic Research Consortium (BARC) type 2–5 bleeding occurred in 2.7% of the 6-month DAPT group and 3.9% of the 12-month or longer DAPT group (p=0.09). In the “Evaluation of short-term dual antiplatelet therapy in patients with acute coronary syndrome treated with a new-generation stent (REDUCE)” trial a composite (ischemia and bleeding) endpoint was non-inferior in 3 months compared with 12 months of DAPT among patients with ACS (De Luca 2019). Once again, a tradeoff was apparent between the risk of bleeding and the risk of thrombosis with numerically fewer bleeding events (3.3% vs 4.0%, p=0.46) associated with a numerically higher incidence of cardiac mortality (1.8% vs 1.1%, p=0.28) and stent thrombosis (1.6% vs 0.8%, p=0.16) with shortened DAPT.

The critical gap facing clinicians is demonstrated by the combination of 1) trials demonstrating that prolonged treatment with DAPT can reduce the incidence of ischemic/thrombotic events at the cost of bleeding; and 2) trials demonstrating that shortened DAPT can reduce the incidence of bleeding at the cost of a greater risk of ischemic events. Consensus guidelines recommend treatment with DAPT after MI and coronary stenting, however, specific guidance on the duration of DAPT is not possible based on available evidence (Bittl 2016). The guideline committee recommended a minimum duration with DAPT of 3 to 6 months but also noted that extension of DAPT beyond 12 months entailed a tradeoff between a risk of bleeding and ischemic events. A precision tool that can be used to guide clinical decision making would improve care. Patients at low risk should benefit from shortened treatment with more powerful antiplatelet therapy whereas patients at high risk should derive greater absolute benefit from long term treatment with more powerful antiplatelet therapy.

